8.2.2 Other Primary Endpoint(s)

None

8.3 Secondary Endpoint(s)

8.3.1 Secondary Efficacy Endpoint(s)

- 8.3.1.1 Improvement in accuracy in left ventricular ejection fraction (LVEF) assessment using DEFINITY® contrast-enhanced over unenhanced echocardiography in subjects with suboptimal echocardiograms

The above primary analyses will be repeated here, but on the subgroup of subjects with suboptimal echocardiograms. There will be no imputation of missing data for this analysis.

- 8.3.1.2 Reduction in inter-reader variability for the assessment of LVEF using DEFINITY® contrast-enhanced versus unenhanced echocardiography

The inter-observer variability among each pair of readers within each imaging modality will be estimated using an intra-class correlation coefficient (ICC). The ICC assesses rating reliability by comparing the variability of different ratings of the same subject with the total variation across all ratings and all subjects. The inter-observer variability in the assessment of LVEF between two readers will be determined by percentage of error. The percentage of error will be calculated using the formula:

Percentage of error = SD between 2 measurements/ mean of the 2 measurements x 100

The mean percentage of error and its 95% confidence interval will be calculated for each pair of readers within each imaging modality.

There will be no imputation of missing data for this analysis.

8.3.1.3 Reduction in inter-reader variability for the assessment of end-diastolic/systolic volumes using DEFINITY® contrast-enhanced versus unenhanced echocardiography

The above analyses used to assess inter-reader variability on LVEF will be carried out, but on end-diastolic/systolic volumes. There will be no imputation of missing data for this analysis.

8.3.1.4 Reduction in inter-reader variability for the assessment of LVEF using DEFINITY® contrast-enhanced versus unenhanced echocardiography in subjects with suboptimal echocardiograms

The above analyses used to assess inter-reader variability on LVEF will be carried out, but on the subgroup of subjects with suboptimal echocardiograms. There will be no imputation of missing data for this analysis.

8.3.1.5 Reduction in inter-reader variability for the assessment of End-Diastolic/Systolic volumes using DEFINITY® contrast-enhanced versus unenhanced echocardiography in subjects with suboptimal echocardiograms

The above analyses used to assess inter-reader variability on LVEF in subjects with suboptimal echocardiograms will be carried out, but on end-diastolic/systolic volumes. There will be no imputation of missing data for this analysis.

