In addition, a safety follow-up phone call will be conducted at 72 ± 24 hours after DEFINITY® administration.

All echocardiography images will be interpreted by 3 experienced independent blinded readers at a central imaging core laboratory. A single, independent, blinded echocardiologist will read each subject's unenhanced echocardiogram as either optimal or suboptimal. This will be independent of the site investigator determination. All CMR images will be read centrally by a single reader. Echocardiographic imaging data will be compiled, analyzed, and stored without knowledge of the CMR findings.

Study Population:

Approximately one hundred and fifty (150) evaluable subjects will be enrolled at approximately 10 US centers. Subjects who have had a 2D echo with or without contrast or other methods (e.g. CMR, MUGA scan) to evaluate screening LVEF within 6 months prior to enrollment (Day 0) may be enrolled. The study population will consist of males and non-pregnant and non-lactating females 18 years-of-age or older.

Duration of Treatment:

Subjects will receive DEFINITY® treatment once as a part of a single day imaging session.

Study Treatment:

DEFINITY® will be administered as a diluted bolus injection. 1.3 mL of activated DEFINITY® will be diluted with 8.7 mL of preservative-free saline to evenly distribute microspheres. An initial injection of up to 3 mL of diluted DEFINITY® will be administered with subsequent injections of 1 to 2 mL, as needed.

Efficacy Assessments:

The primary endpoint is to demonstrate an improvement in LVEF accuracy from unenhanced imaging to imaging with DEFINITY® contrast enhancement using CMR as the truth standard.

The secondary endpoints are to:

1. Demonstrate improvement in accuracy in left ventricular ejection fraction (LVEF) assessment using DEFINITY® contrast-enhanced over unenhanced echocardiography in subjects with suboptimal echocardiograms.
2. Demonstrate a reduction in inter-reader variability for the assessment of LVEF using DEFINITY® contrast-enhanced versus unenhanced echocardiography.
3. Demonstrate a reduction in inter-reader variability for the assessment of end-diastolic/systolic volumes using DEFINITY® contrast-enhanced versus unenhanced echocardiography.
4. Demonstrate a reduction in inter-reader variability for the assessment of LVEF using DEFINITY® contrast-enhanced versus unenhanced echocardiography in subjects with suboptimal echocardiograms.

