2.2 Secondary Objectives

The secondary objectives of the study are to:

1. Demonstrate improvement in accuracy in left ventricular ejection fraction (LVEF) assessment using DEFINITY® contrast-enhanced over unenhanced echocardiography in subjects with suboptimal echocardiograms.
2. Demonstrate a reduction in inter-reader variability for the assessment of LVEF using DEFINITY® contrast-enhanced versus unenhanced echocardiography.
3. Demonstrate a reduction in inter-reader variability for the assessment of end-diastolic/systolic volumes using DEFINITY® contrast-enhanced versus unenhanced echocardiography.
4. Demonstrate a reduction in inter-reader variability for the assessment of LVEF using DEFINITY® contrast-enhanced versus unenhanced echocardiography in subjects with suboptimal echocardiograms.
5. Demonstrate a reduction in inter-reader variability for the assessment of end-diastolic/systolic volumes using DEFINITY® contrast-enhanced versus unenhanced echocardiography in subjects with suboptimal echocardiograms.

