8.2. Secondary Efficacy Endpoint(s) and Analyses

8.2.1. Improvement in accuracy in LVEF assessment using DEFINITY® contrast-enhanced over unenhanced echocardiography in subjects with suboptimal echocardiograms

The primary endpoint analysis will be repeated in the subset of subjects with suboptimal echocardiograms. This will include all primary analyses described in sections 8.1 and 8.1.1, excluding the supportive analyses at the end of section 8.1. The study is not powered to reject the primary endpoint null hypothesis, so the focus is more on the estimate of $\mu_D - \mu_U$, on Bland-Altman plots and on the Deming regression for each blinded reader. There will be no imputation of missing LVEF data for this analysis.

8.2.2. Reduction in inter-reader variability for the assessment of LVEF using DEFINITY® contrast-enhanced versus unenhanced echocardiography

The inter-reader variability among each pair of readers within each imaging modality will be estimated using an intra-class correlation (ICC) and its two-sided 95% CI. The ICC assesses rating reliability by comparing the variability of different ratings of the same subject with the total variation across all ratings and all subjects. The inter-observer variability in the assessment of LVEF between two readers will be determined by percentage of error. The percentage of error will be calculated using the following formula:

$$\text{Percentage of error} = (\text{SD between 2 measurements} / \text{mean of the 2 measurements}) \times 100$$

The mean percentage of error and its 95% CI will be calculated for each pair of readers within each imaging modality. The pairwise ICCs and percentages of error differences will be compared descriptively between contrast-enhanced and unenhanced echocardiography.

In addition, specific to only section 8.2.2, there will also be a separate ICC analysis to assess intra-reader variability as approximately 10% of all echo results will be re-read by each reader.

This document is confidential.

8.2.3. Reduction in inter-reader variability for the assessment of end-diastolic/systolic volumes using DEFINITY® contrast-enhanced versus unenhanced echocardiography

The same analysis used to assess inter-reader variability on LVEF (section 8.2.2) will be conducted for end-diastolic/systolic volumes.

8.2.4. Reduction in inter-reader variability for the assessment of LVEF using DEFINITY® contrast-enhanced versus unenhanced echocardiography in subjects with suboptimal echocardiograms

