
The same analysis used to assess inter-reader variability on LVEF (section 8.2.2) will be conducted for the subgroup of subjects with suboptimal echocardiograms.

8.2.5. Reduction in inter-reader variability for the assessment of end-diastolic/systolic volumes using DEFINITY® contrast-enhanced versus unenhanced echocardiography in subjects with suboptimal echocardiograms

The same analysis used to assess inter-reader variability on LVEF (section 8.2.4) for the subgroup of subjects with suboptimal echocardiograms will be conducted for end-diastolic/systolic volumes.

This document is confidential.

9. Safety

The population used for safety analyses will be the Safety population (SP). Safety will be assessed on the basis of adverse event (AE) or serious adverse event (SAE) reports, physical examinations, and vital signs.

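### Inter-reader variability is estimated only by pair of readers, with no overall three-reader estimate and no rule for pairs that disagree

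*Protocol*

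**What the plan says.** The reading design is fully crossed. The protocol synopsis (Study Design) states: "All echocardiography images will be interpreted by 3 experienced independent blinded readers at a central imaging core laboratory".

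Protocol 2.2 frames the inter-reader objectives as directional questions. Objective 2 reads: "Demonstrate a reduction in inter-reader variability for the assessment of LVEF using DEFINITY® contrast-enhanced versus unenhanced echocardiography". Objectives 3 to 5 ask the same of the volumes, and of LVEF and the volumes in subjects with suboptimal echocardiograms.

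The analyses are all pairwise:

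- Protocol 8.3.1.2: "The inter-observer variability among each pair of readers within each imaging modality will be estimated using an intra-class correlation coefficient (ICC").
- SAP 8.2.2 adds an interval: "The inter-reader variability among each pair of readers within each imaging modality will be estimated using an intra-class correlation (ICC) and its two-sided 95% CI".
- Percentage of error, the second measure, is also by pair (Protocol 8.3.1.2): "The mean percentage of error and its 95% confidence interval will be calculated for each pair of readers within each imaging modality".
- The same analysis is carried to the volumes (Protocol 8.3.1.3): "The above analyses used to assess inter-reader variability on LVEF will be carried out, but on end-diastolic/systolic volumes". It is also carried to the suboptimal subgroup (SAP 8.2.4): "The same analysis used to assess inter-reader variability on LVEF (section 8.2.2) will be conducted for the subgroup of subjects with suboptimal echocardiograms".
- The modalities are compared as follows (SAP 8.2.2): "The pairwise ICCs and percentages of error differences will be compared descriptively between contrast-enhanced and unenhanced echocardiography".

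**The concern.** Each objective poses one question per measurement, and the plan returns three answers to it. The pairs 1-2, 1-3 and 2-3 share readers, so the answers are correlated, yet they can still differ in sign. Neither document gives an average over pairs, a lead pair, or a reading of a mixed pattern. The rule that two of three readers must succeed (Protocol 8.2.1, SAP 8.1) belongs to the primary paired t-test only.

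What is at stake is the claim that a reduction has been demonstrated. With no estimate named in advance, the weight given to each pair is decided after the results are known, and a report could stress the favourable ones. The suboptimal subgroup (objectives 4 and 5) is the most exposed, because it is smaller and its size is not given.

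**Working it through.** **Is a three-reader estimate planned anywhere?** The other ICCs in the documents are echo against CMR for each reader (Protocol 8.2.1, SAP 8.1.1) and intra-reader agreement on about 10% re-reads (SAP 8.2.2). The sentence in Protocol 8.3.1.2 and SAP 8.2.2 that relates variability within a subject to total variation describes what an ICC is; it follows the pairwise sentence and plans no further model. So the answer is no.

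**Count of contrasts.** Three pairs × three measurements (LVEF, EDV, ESV) = 9 ICC contrasts in all subjects. The same 9 in suboptimal subjects make 18. Percentage of error adds as many again.

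**The plan's own figure.** The documents give no power or precision target for the inter-reader ICCs. The only design figure is for the primary test: difference 2.75, SD 10, two-sided 0.05, 150 enrolled and about 143 evaluable. Noncentral-t power at n = 143 is 90.4%, so the stated 90% reproduces. It is used here only to fix n = 143.

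**Inputs for the simulation.** From the documents: three crossed readers, two modalities, n = 143. Assumed: between-subject LVEF SD 14; unenhanced reader-error SD 6; enhanced reader-error SD 6, 5.5, 5 or 4; errors independent across readers and modalities; readers exchangeable; suboptimal subgroup of 70 or 45.

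**Formula.** Two-way absolute-agreement ICC, with k readers and mean squares for subjects (MSR), readers (MSC) and error (MSE):

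ICC = (MSR − MSE) / [MSR + (k − 1)·MSE + k·(MSC − MSE)/n]

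Under these assumptions its expected value is about 14² / (14² + error SD²). For unenhanced imaging this is 196/(196 + 36) = 0.845. For an enhanced error SD of 5.5 it is 196/(196 + 30.25) = 0.866, a contrast of 0.021.

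**Share of trials in which the three pairwise contrasts do not all have the same sign:**

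| Enhanced error SD | Expected ICC contrast | n = 143 | n = 70 | n = 45 |
|---|---|---|---|---|
| 6 (no gain) | 0 | 64% | 63% | 62% |
| 5.5 | 0.021 | 40% | 49% | 52–55% |
| 5 | 0.042 | 8% | 23% | 33% |
| 4 | 0.080 | 0% | 0.4% | 2% |

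Repeat runs agree to within about three percentage points. With between-subject SD 13 the n = 143 column becomes 64%, 40%, 9% and about 0%.

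**Precision (n = 143, error SD 6 to 5.5).** The SD of the enhanced-minus-unenhanced ICC contrast is about 0.024 to 0.025 for one pair and 0.017 for three readers. The simple average of the three pairwise contrasts also has SD 0.017, and its correlation with the three-reader contrast is 0.9998.

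**One discordant reader.** With between-subject SD 13, unenhanced error SDs 6, 6, 6 and enhanced SDs 4, 4, 9, the mean pairwise contrasts are +0.09, −0.05 and −0.05. The signs split in 98% of trials at n = 143, and the three-reader contrast averages −0.007.

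**The case against.** The strongest reply is that the plan is openly descriptive. It has no test, alpha or success criterion for these objectives, and a mixed pattern is then a reportable finding. The SAP gives an interval for each pairwise ICC and each mean percentage of error. Pairwise results are also informative in their own right: in the discordant-reader case the split is signal, and a single ICC near zero change would hide it. All of this stands, and it is why the pairwise results should be kept.

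Three stronger readings are tempting, and the documents do not support them:

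- **That the planned analysis discards data, or that a three-reader ICC is about 30% more precise.** That compares one pair with three readers. The plan reports all three pairs, which together hold every reading, and their average matches the three-reader ICC almost exactly.
- **That the pairs will often disagree.** This is so for no gain or a small gain, or in a small subgroup. At n = 143 it is uncommon (8%) once reader-error SD falls by one sixth, and it does not occur at a fall of one third, provided the readers are alike.
- **That objectives 2 to 5 are left without an answer.** They get descriptive answers. Under the 6 to 5.5 setting, even counting whether two of the three pairs favour contrast gives the right direction in 88% of trials.

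Protocol 3.1 also refers to further analyses in the Image Review Charter, which is not among the documents. A summary could be defined there, but the endpoint analyses are specified in the protocol and SAP.

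**Conclusion.** The point holds as a gap in pre-specification. Objectives 2 to 5 are analysed only by pair, compared descriptively, with no overall estimate and no rule for pairs that point in different directions. The risk of a split at n = 143 runs from about 64% with no gain to 0% for an error SD of 6 to 4. At an assumed subgroup of 45 it runs from about 62% to 2%. These figures rest on assumed SDs, exchangeable readers and an assumed subgroup size. The absence of a summary estimate does not depend on them. The matter is minor and does not touch the primary endpoint, type I error or sample size.

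**What to change.** In Protocol 8.3.1.2 and SAP 8.2.2, carried to Protocol 8.3.1.3 to 8.3.1.5 and SAP 8.2.3 to 8.2.5:

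- Name as the lead estimate one three-reader absolute-agreement ICC per modality and measurement, from a two-way subject-by-reader model.
- Give a 95% CI for each modality and for the enhanced-minus-unenhanced difference, for example by bootstrapping subjects so that the pairing of modalities and readers is kept. An interval per modality alone would not address the difference that the objective asks about.
- Base the statement for each objective on that difference: one for LVEF, and one each for EDV and ESV.
- Keep the pairwise ICCs and percentage of error as supportive results, so that a discordant reader remains visible.

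The cost is SAP wording, one extra model per modality and measurement, and a bootstrap per measurement. No new reads or subjects are needed.

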4 STUDY POPULATION

Approximately one hundred and fifty (150) evaluable subjects who have previously undergone a 2D echocardiogram with or without contrast or other assessment (CMR, MUGA scan) will be enrolled in this trial. The study population will consist of male and female subjects 18 years of age or older.

Enrollment will be stratified according to CMR LVEF to achieve an approximately even distribution across four subgroups (LVEF >50, 41-50, 30-40, <30%). LVEF for screening purposes will be determined by the investigator and based on measurements with 2D echo or other methods (e.g. CMR, MUGA scan) obtained within 6 months prior to enrollment (Day 0). Subjects with optimal and sub-optimal echocardiograms will be enrolled. Suboptimal echocardiograms will be based on the site investigator's evaluation of the unenhanced echocardiography images obtained on Day 0. An echocardiogram is considered suboptimal if 2 or more segments of the ventricular border are classified as not adequately visualized in any one of the 3 apical views.

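### Percentage of error between readers divides by each modality's own mean, so a level shift alone can move it, and no inter-reader measure in LVEF points or mL is planned beside it

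*Protocol*

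**What the plan says.** Four of the five secondary objectives aim to show lower inter-reader variability with contrast: for LVEF and for end-diastolic and end-systolic volumes (EDV, ESV), each in all subjects and in those with suboptimal echocardiograms.

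Protocol 8.3.1.2 gives two measures for each pair of readers. The first is the ICC. The second is introduced with the words "The inter-observer variability in the assessment of LVEF between two readers will be determined by percentage of error" and defined as "Percentage of error = SD between 2 measurements/ mean of the 2 measurements x 100". It is summarised by modality: "The mean percentage of error and its 95% confidence interval will be calculated for each pair of readers within each imaging modality". Protocol 8.3.1.3 to 8.3.1.5 carry both measures to the volumes and to the suboptimal subgroup.

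SAP 8.2.2 keeps the formula, adds a 95% confidence interval for the ICC, and states how the modalities are set against each other: "The pairwise ICCs and percentages of error differences will be compared descriptively between contrast-enhanced and unenhanced echocardiography". SAP 8.2.3 extends this to volumes: "The same analysis used to assess inter-reader variability on LVEF (section 8.2.2) will be conducted for end-diastolic/systolic volumes". SAP 8.2.4 and 8.2.5 do the same for the suboptimal subgroup.

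Bias, SD of differences, RMSE and Bland-Altman limits are specified only for echo against CMR (protocol 8.2.1, SAP 8.1.1). Neither document plans a between-reader figure in LVEF points or mL.

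**The concern.** Both modalities image the same hearts, but percentage of error uses a different denominator for each: the mean of that modality's own two readings. The plan itself allows for a difference in level. Protocol 1.1 names poor discrimination of the endocardial border as a main source of echo inaccuracy, protocol 6.8.2 obtains volumes by tracing that border, and protocol 8.2.1 estimates LVEF bias against CMR separately for each modality. If contrast moves the traced border systematically, the denominator moves too.

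Percentage of error then mixes two things: how far apart the readers are, and how high they both read. If enhanced volumes read larger, it falls with no gain in agreement. If enhanced LVEF reads lower, it rises and can hide a real gain. A figure in measurement units would separate the two, and none is planned.

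**Working it through.** **Inputs.** The formula is from protocol 8.3.1.2 and SAP 8.2.2. The documents attach no expected value, margin or power to percentage of error, so there is no planned figure to reproduce for it. Their only power figure, 90% for the primary paired t-test (difference 2.75, SD 10, 150 enrolled, about 143 evaluable), reproduces at 90.4% with n = 143 and does not depend on this point. All levels, disagreements and shifts below are assumptions.

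**Step 1: the formula for two readers.** The SD of two readings is |r1 − r2|/√2, so percentage of error = 100 × (|r1 − r2|/√2) / mean.

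**Step 2: shift the mean, hold the disagreement.** If the modality's mean is multiplied by (1 + k) and |r1 − r2| stays the same, percentage of error is multiplied by 1/(1 + k):

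- k = +10%: 1/1.1 − 1 = −9.1%
- k = +20%: 1/1.2 − 1 = −16.7%
- k = +30%: 1/1.3 − 1 = −23.1%
- k = −10%: 1/0.9 − 1 = +11.1%

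**Step 3: examples in units.**

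| Measure | Disagreement | SD in units | Percentage of error, unshifted | After shift |
|---|---|---|---|---|
| EDV | 15 mL | 10.6 mL | 10.6/120 = 8.84% | 10.6/144 = 7.37% (+20%) |
| ESV | 10 mL | 7.07 mL | 7.07/60 = 11.79% | 7.07/72 = 9.82% (+20%) |
| LVEF 45 | 5 points | 3.54 points | 3.54/45 = 7.86% | 7.37% (+3 points), 8.42% (−3 points) |
| LVEF 25 | 5 points | 3.54 points | 3.54/25 = 14.14% | 12.63% (+3 points), 16.07% (−3 points) |

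The SD in units is the same before and after the shift in every row.

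**Step 4: the two planned measures together.** One set of 143 subjects was simulated for each measure, and a constant was added to both readers' values.

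- EDV (assumed mean 150 mL, SD 45 mL, reader error SD 12 mL). Shifts of 0, +15 and +30 mL give percentage of error 6.70%, 5.95% and 5.36%. Mean absolute disagreement stays at 12.43 mL and ICC at 0.925.
- LVEF (spread evenly over the four enrolment bands, reader error SD 4 points). Shifts of −3, 0, +3 and +5 points give 11.0%, 9.89%, 9.01% and 8.51%. Mean absolute disagreement stays at 4.91 points and ICC at 0.903.

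The ICC is therefore unmoved by a constant shift. It can move if the spread between subjects changes. With the same assumed EDV values, ICC = 45²/(45² + 12²) = 2025/2169 = 0.934. If every heart reads 20% larger with the same 12 mL error, it is (1.44 × 2025)/(1.44 × 2025 + 144) = 2916/3060 = 0.953.

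**Step 5: the reverse case.** If reader error is proportional to size, the absolute scale has the opposite weakness. An 8% coefficient of variation is 9.6 mL at 120 mL and 11.5 mL at 144 mL. The SD in mL rises by 20% with no loss of relative agreement, and so does that SD divided by the subject's CMR volume.

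**The case against.** The strongest case against the point has four parts.

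- **Percentage of error is not the whole endpoint.** The pairwise ICC comes first in protocol 8.3.1.2, is the only inter-reader measure in the synopsis, and has a confidence interval in SAP 8.2.2. Under a constant shift a reader would see percentage of error fall and ICC stay flat. This stands, and it limits the point to one of two measures. It does not close the gap, because ICC depends on the spread between subjects and never states the disagreement in mL or LVEF points.
- **The comparison is descriptive and secondary.** No between-modality test or success rule is attached. This stands in full.
- **A coefficient of variation is a reasonable choice when disagreement grows with size.** For volumes this stands: the documents do not say which error model applies, and step 5 shows that replacing the percentage by mL would only exchange one weakness for another. For LVEF the argument is weaker. LVEF is one minus ESV/EDV, so if relative volume errors are constant (an assumption), the SD of LVEF is proportional to (1 − LVEF) and grows as LVEF falls. LVEF points are also the scale of the primary endpoint.
- **A level shift would be partly visible.** LVEF bias by modality is planned, and SAP 8 says all efficacy parameters will be summarised. The protocol also refers to further analyses in an Image Review Charter that is not among the documents. So the absence of an absolute measure is established for the protocol and SAP only.

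A reader might also infer that spreading enrolment down to LVEF below 30% biases the comparison, because the same 3-point SD is 12.0% at LVEF 25 and 5.0% at 60. The documents do not support that. Each subject is imaged both ways, so the weighting applies to both modalities and creates no difference between them by itself. It does make the mean percentage more sensitive to a shift at low LVEF, as the table shows.

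**Conclusion.** The point holds for percentage of error. At equal absolute disagreement it changes with the modality's mean level, by relative falls of 9%, 17% and 23% for readings 10%, 20% and 30% larger, and by a rise of 11% for readings 10% smaller. The algebra follows from the written formula. The size in this trial is unknown, because the documents give neither size nor direction for a shift.

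It would be tempting to conclude that the reproducibility objectives are confounded as a whole, or that the measure is tilted towards DEFINITY. Neither follows. The ICC is reported alongside and does not respond to a constant shift, and a downward shift in the enhanced readings would count against DEFINITY. The primary analysis, its power and the interim sample-size rule are untouched. This is a cheap improvement to four descriptive secondary objectives and does not threaten the trial's main conclusion.

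**What to change.** **LVEF (SAP 8.2.2 and 8.2.4).** For each reader pair and modality, report the within-subject inter-reader SD in LVEF points with a 95% confidence interval, and make this the figure compared between modalities beside the ICC. Keep percentage of error as supportive.

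**Volumes (SAP 8.2.3 and 8.2.5).** For EDV and ESV, report the inter-reader SD in mL beside percentage of error, with the mean level by modality in the same table. State that variability will be described as reduced only if both the mL figure and the percentage fall.

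**Cost.** SAP wording before database lock and one or two extra table columns, with no new data or reads. The downside is a possible mixed result for volumes if reader error is proportional to size; the mean level by modality would help to explain it.
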